3.3 SECONDARY OBJECTIVES

See Table 7.

3.4 SECONDARY ENDPOINTS

Table 7: Secondary Objectives and Associated Endpoints

Phase 2 Secondary Objectives Phase 2 Secondary Endpoints	
1. Evaluate the safety and tolerability of INO-4800 administered by ID	1a. Incidence of solicited and unsolicited injection site reactions
injection followed immediately by EP	1b. Incidence of solicited and unsolicited systemic adverse events (AEs) by system organ class (SOC), preferred term (PT), severity and relationship to investigational product
	1c. Incidence of serious adverse events (SAEs)
	1d. Incidence of adverse events of special interest (AESIs)
Phase 3 Secondary Objectives	Phase 3 Secondary Endpoints
1. Evaluate the safety and tolerability of INO-4800	 Incidence of solicited and unsolicited injection site reactions
	1b. Incidence of solicited and unsolicited systemic adverse events (AEs) by system organ class (SOC), preferred term (PT), severity and relationship to investigational product
	1c. Incidence of serious adverse events (SAEs)
	1d. Incidence of adverse events of special interest (AESIs)
	1e. Incidence of all-cause mortality
2. Evaluate efficacy of INO-4800 in the prevention of COVID-19 disease according to degrees of disease severity in subjects who are SARS-	2a. Incidence of non-severe COVID-19 disease in SARS-CoV-2 seronegative subjects starting 14 days after completion of the 2-dose regimen until EOS
CoV-2 seronegative at baseline	2b. Incidence of severe COVID-19 disease in SARS- CoV-2 seronegative subjects starting 14 days after completion of the 2-dose regimen until EOS

		2c. Incidence of deaths due to COVID-19 in SARS- CoV-2 seronegative subjects starting 14 days after completion of the 2-dose regimen until EOS
3.	Evaluate the cellular and humoral immune response to INO-4800	3a. Antigen-specific cellular immune response measured by IFN-gamma ELISpot
		3b. Neutralizing antibody response measured by a pseudovirus-based neutralization assay
4.	Evaluate the efficacy of INO-4800 in the prevention of COVID-19 disease in subjects who are SARS- CoV-2 seropositive at baseline	 Incidence of virologically-confirmed COVID-19 disease starting 14 days after completion of the 2-dose regimen until 12 months post-dose 2 (End of Study (EOS)) in subjects who are SARS- CoV-2 seropositive at baseline

3.5 **EXPLORATORY OBJECTIVE**

See Table 8.

3.6 EXPLORATORY ENDPOINTS

Table 8: Exploratory Objectives and Associated Endpoints

Pł	Phase 2 Exploratory Objective Phase 2 Exploratory Endpoints	
1.	Evaluate the expanded immunological profile of antibody	 Antigen-specific cellular immune response measured by flow cytometry.
	response and T cell immune response	1b. Expanded immunological profile which may include additional assessments of T and B cell numbers and molecular changes by measuring immunologic proteins and mRNA levels of genes of interest as determined by sample availability
Pł	nase 3 Exploratory Objective	Phase 3 Exploratory Endpoints
1.	Evaluate the efficacy of INO-4800 in the prevention of COVID-19 disease from SARS-CoV-2 variants in subjects who are SARS-CoV-2 seronegative at baseline	 Incidence of virologically-confirmed COVID-19 disease from a SARS-CoV-2 variant starting 14 days after completion of the 2-dose regimen until 12 months post-dose 2 (End of Study (EOS)) in subjects who are SARS-CoV-2 seronegative at baseline
2.	Evaluate the efficacy of INO-4800 in the prevention of SARS-CoV-2 asymptomatic infection in subjects who are SARS-CoV-2 seronegative at baseline	2. Incidence of SARS-CoV-2 asymptomatic infections in SARS-CoV-2 seronegative subjects starting 14 days after completion of the 2-dose regimen until EOS
3.	Evaluate the immunological profile by assessing both antibody response and T cell immune response	 3a. SARS-CoV-2 Spike glycoprotein antigen- specific binding antibody levels 3b. Antigen-specific cellular immune response measured by flow cytometry
4.	Evaluate antibody persistence	 4a. SARS-CoV-2 Spike glycoprotein antigen specific binding antibody levels at Week 30 or later. 4b. Neutralizing antibody response measured by a pseudovirus-based neutralization assay at Week 30 or later

INO-4800	COVID19-311
Inovio Pharmaceuticals, Inc.	Clinical Protocol

3.7 EFFICACY ASSESSMENT (PHASE 3 SEGMENT ONLY)

Subjects will receive either active investigational product (INO-4800, dose selected from the Phase 2 segment) or placebo (placebo for INO-4800) in a 2-dose regimen administered intradermally followed immediately by EP on Days 0 and 28. Subjects will be monitored through regularly scheduled clinic visits and phone calls throughout the trial. Subjects will be regularly tested for SARS-CoV-2 infection using serologic testing. If COVID-19 disease is suspected based on symptoms or laboratory testing, site personnel will arrange for a clinic visit. Subjects with symptom(s) or a positive SARS-CoV-2 test result will be reviewed by the independent blinded EAC.

The mechanism for review and confirmation of cases will be outlined in an EAC Charter.

3.7.1 CASE DEFINITION FOR VIROLOGICALLY-CONFIRMED COVID-19 DISEASE:

- Positive testing by SARS-CoV-2 RT-PCR assay (performed at central lab*) with fever (temperature of 100.4°F/38.0°C or higher), or
- Positive testing by SARS-CoV-2 RT-PCR assay (performed at central lab*) with any of the following COVID-19 related symptoms:
 - Feeling feverish or chills
 - Cough
 - Shortness of breath or difficulty breathing
 - Fatigue
 - Muscle or body aches
 - Headache
 - New loss of taste or smell
 - Sore throat
 - Congestion or runny nose
 - Nausea or vomiting
 - Diarrhea

*Local lab results will be accepted if the subject is hospitalized and a sample is not able to be obtained for analysis at central lab.

3.7.1.1 Case Definition for Severe COVID-19

- Confirmed COVID-19 disease (per Section 3.7.1) with any of the following:
 - a. Clinical signs at rest indicative of severe systemic illness (respiratory rate ≥ 30 per minute, heart rate ≥ 125 per minute, SpO2 ≤ 93% on room air at sea level or PaO2/FiO2 < 300 mm Hg),
 - b. Respiratory failure (defined as needing high-flow oxygen, noninvasive ventilation, mechanical ventilation or ECMO),
 - c. Evidence of shock (SBP < 90 mm Hg, DBP < 60 mm Hg, or requiring vasopressors),
 - d. Significant acute renal, hepatic, or neurologic dysfunction,
 - e. Admission to an ICU, or
 - f. Death.

3.7.1.2 Case Definition for Non-Severe COVID-19

- Confirmed COVID-19 disease (per Section 3.7.1);
- Does not meet the case definition of Severe COVID-19 disease (Section 3.7.1.1)

INO-4800	COVID19-311
Inovio Pharmaceuticals, Inc.	Clinical Protocol

3.7.2 CASE DEFINITION FOR SARS-COV-2 ASYMPTOMATIC INFECTION

Positive testing by SARS-CoV-2 serologic assay (performed at central lab);

• Without clinical signs or symptoms of COVID-19 disease since the previous negative serologic test.

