4.2.2 PHASE 3 SEGMENT

- Acute febrile illness with temperature ≥100.4°F (38.0°C) or acute onset of upper or lower respiratory tract symptoms (e.g., cough, shortness of breath, sore throat) on Day 0 prior to dosing;
- Positive serologic test for SARS-CoV-2 at Screening (after approximately 402 subjects positive for SARS-CoV-2 serologic test are randomized, this criterion will apply to all remaining subjects);
- c. Pregnant or breastfeeding, or intending to become pregnant or intending to father children starting from the Screening visit until the last dose;
- d. Positive urine pregnancy test during screening or immediately prior to dosing;
- e. Known history of uncontrolled HIV based on a CD4 count less than 200 cells/mm³ or a detectable viral load within 3 months prior to screening;
- f. Is currently participating or has participated in a study with an investigational product within 30 days prior to Day 0 (documented receipt of placebo in a previous trial would be permissible for trial eligibility);
- g. Previous or planned receipt of an investigational (including Emergency Use Authorization (EUA) or local equivalent authorization) or licensed vaccine for prevention or treatment of COVID-19, MERS or SARS (documented receipt of placebo in previous trial would be permissible for trial eligibility);
- h. Immunosuppression as a result of underlying illness or treatment including:
 - Primary immunodeficiencies (conditions including hypothyroidism, Hashimoto's thyroiditis and vitiligo are allowed);
 - Long term use (≥7 days) of oral or parenteral glucocorticoids at a dose of ≥20 mg/day of prednisone equivalent (use of inhaled, topical, nasal, otic, and ophthalmic corticosteroids are allowed) in the past 6 months;
 - Current or anticipated use of disease modifying doses of systemic anti-rheumatic drugs (e.g., azathioprine, cyclophosphamide, cyclosporine, methotrexate) and biologic disease modifying drugs such as TNF-α inhibitors (e.g., infliximab, adalimumab or etanercept) or others;
 - History of solid organ or bone marrow transplantation;
 - History of or current receipt of any other clinically significant immunosuppressive drugs
 - Diagnosis of an autoimmune disease that may jeopardize the safety of the subject or require therapy that would interfere with study assessments or endpoint evaluation, or otherwise impact the validity of the study results.

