6.1.2.8 COVID-19 Convalescent Visit

Phase 2 and Phase 3 segments: For subjects with confirmed SARS-CoV-2 infection during the trial, a convalescent visit should be scheduled approximately 28 days after symptom onset, or in the absence of symptoms, after the collection date of a positive SARS-CoV-2 test. If symptoms are ongoing at 28 days after symptom onset, the site should follow up with the subject via phone call or unscheduled visit after symptom resolution or stabilization.

The following evaluations will be performed at this visit:

- Collect all present and/or new or ongoing AEs (Section 6.4.4); Only SAEs, AESIs and MAAEs will be reported after the Day 56 Visit;
- Document any present conditions and concomitant illnesses;
- Record current concomitant medications/treatments (Section 6.4.6);
- Targeted physical examination (Section 6.4);
- Record vital signs (Section 6.4);
- Collect whole blood and serum for cellular and humoral immunology assessment (Phase 3 cellular immunology collection at selected sites only) (Section 6.5);

Phase 2 segment only:

• Collect nasal swabs and saliva for SARS-CoV-2 RT-PCR detection (Section 6.4.8).

Phase 3 segment only:

• Collect serum for SARS-CoV-2 antibody testing (Section 6.4.8).

6.2 **INFORMED CONSENT**

All subjects must sign the informed consent prior to participating in any clinical trial-related procedures. The informed consent documentation must be in compliance with applicable regulations and GCP. Qualified clinical trial personnel will:

- Meet with prospective clinical trial subjects;
- Explain the clinical trial;

INO-4800	COVID19-311
Inovio Pharmaceuticals, Inc.	Clinical Protocol

- Provide clinical trial subjects with an Informed Consent Form (ICF) that includes the following in a language that is understandable to the subject:
 - Screening test(s) description;
 - Eligibility criteria for entering the clinical trial;
 - Clinical trial treatments and follow-up procedures description;
 - Explanation of the clinical trial, including but is not limited to:
 - Clinical trial objectives;
 - Potential benefits and risks;
 - Discomforts/inconveniences;
 - Subject's rights and responsibilities.

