6.4.8 SARS-CoV-2 TESTING

Phase 2 segment:

SARS-CoV-2 antibody and RT-PCR testing will be used during screening to test for previous or current SARS-CoV-2 infection. During the trial, subjects who report symptoms suggestive of COVID-19 will be assessed at a COVID-19 assessment visit in the clinic or subject's vehicle or at the subject's home. During this visit, nasal swabs and saliva will be collected to detect SARS-CoV-2 using the RT-PCR assay. Genotyping may also be performed. If the subject is confirmed to be COVID-19 positive, a follow-up nasal swab and saliva will be collected to detect SARS-CoV-2 using the RT-PCR assay at the COVID-19 convalescent visit.

Phase 3 segment:

SARS-CoV-2 antibody testing will be used during screening to test for previous SARS-CoV-2 infection and during each subsequent visit (see Table 4: Schedule of Events) to identify SARS-CoV-2 infections that may occur regardless of symptoms between study visits.

SARS-CoV-2 RT-PCR testing will be conducted on nasopharyngeal specimens collected at Day 0. The Day 0 SARS-CoV-2 RT-PCR results will not be required prior to dosing on that day.

For subjects who are seronegative at baseline, if at any time during the trial, either the SARS-CoV-2 antibody or an RT-PCR test result is positive, the subject will be notified of the result and will be evaluated at a COVID-19 assessment visit. During that visit, which may be conducted in the clinic, from the subject's vehicle, or in the subject's home, nasopharyngeal swabs will be collected to detect SARS-CoV-2 using the RT-PCR assay. Genotyping may also be performed on the sample(s) collected at the COVID-19 assessment visit.

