8.5.9 EXPLORATORY ANALYSES

8.5.9.1 Efficacy

Phase 3 segment

The exploratory efficacy endpoints will be analyzed in the same manner as the primary hypothesis, but with a 95% CI and without the hypothesis test p-value.

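### A single positive serology is enough to count an asymptomatic infection, so false positives over repeat tests would pull this exploratory efficacy estimate toward zero

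*Protocol*

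**What the plan says.** Section 3.7.2 of the protocol has two conditions for an asymptomatic infection: "Positive testing by SARS-CoV-2 serologic assay (performed at central lab"), and "Without clinical signs or symptoms of COVID-19 disease since the previous negative serologic test". It has no third condition. By contrast, the symptomatic case definition in 3.7.1 needs a positive RT-PCR together with fever or a listed symptom.

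The endpoint is exploratory (section 3.6). It covers "infections in SARS-CoV-2 seronegative subjects starting 14 days after completion of the 2-dose regimen until EOS". Under 8.5.9.1, "The exploratory efficacy endpoints will be analyzed in the same manner as the primary hypothesis", with a 95% CI and no p-value.

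On testing, 6.4.8 states that "SARS-CoV-2 antibody testing will be used during screening to test for previous SARS-CoV-2 infection and during each subsequent visit". The Phase 3 schedule (Table 4) places serology at Screening and Days 0, 28, 42, 126, 210, 294 and 393. If, in a baseline-seronegative subject, "either the SARS-CoV-2 antibody or an RT-PCR test result is positive", an assessment visit with a nasopharyngeal RT-PCR swab follows. Section 3.7 sends every positive test to the blinded adjudication committee and leaves the mechanism to its charter. Section 7.11 describes that committee's determination as whether a case is confirmed COVID-19 disease.

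**The concern.** Most of the 6714 baseline-seronegative subjects will stay uninfected, and each is tested repeatedly. When one positive is enough, the chance of at least one false positive grows with every visit. False positives of this kind do not depend on treatment. They add the same proportion of spurious cases to each arm, move the risk ratio toward 1 and understate efficacy against silent infection. Because the endpoint is analysed by the primary method, the Clopper-Pearson interval would be computed on the inflated counts and would look precise around an attenuated value.

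The material for a better rule is largely collected already (the triggered swab, later serology visits, stored serum), but 3.7.2 gives it no role. As written, a subject with one positive antibody result, a negative swab and negative serology at every later visit is a case.

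**Working it through.** **Inputs from the protocol.** 6714 seronegative subjects, 4476 vaccine and 2238 placebo (Table 2); attack rate 3.7% and assumed efficacy 60% against symptomatic disease (8.6); asymptomatic share of infections possibly as high as 80% (1.2).

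**Assumed, because the protocol gives no figure.** Per-test specificity 99.0%, 99.5% or 99.8%; a 40% asymptomatic share as a lower scenario; the same 60% efficacy against asymptomatic infection; independent errors; all tests completed.

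**The plan's own figure.** 2238 × 0.037 + 4476 × 0.037 × 0.4 = 82.8 + 66.2 = 149.05, which reproduces the stated 149 cases and shows that 3.7% acts as the placebo risk.

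**Number of tests.** The window opens 14 days after dose 2. Days 126, 210, 294 and 393 lie clearly inside it. Day 42 is nominally its first day, but note k to Table 4 allows that visit from 10 days after the Day 28 visit, so it can precede the window. The count is therefore four, or five with Day 42.

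**False positives.** With T tests, f = 1 − specificity^T, and the expected false cases if nobody were infected are 6714 × f:

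| Specificity | Four tests | Five tests |
|---|---|---|
| 99.0% | 265 | 329 |
| 99.5% | 133 | 166 |
| 99.8% | 54 | 67 |

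**True asymptomatic cases.** For share s, placebo risk a = 0.037 × s/(1 − s), and cases = 2238a + 4476 × 0.4a.
- s = 40%: a = 0.0247, about 99 cases.
- s = 80%: a = 0.148, about 596 cases.

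**Observed efficacy for a true 60%.** 1 − [0.4a + (1 − 0.4a)f] / [a + (1 − a)f].

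Example (40% share, 99.0%, five tests): f = 0.0490; placebo 0.0247 + 0.9753 × 0.0490 = 0.0725; vaccine 0.0099 + 0.9901 × 0.0490 = 0.0584; efficacy 1 − 0.0584/0.0725 = 19%.

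| Specificity | 40% share, five tests | 40%, four | 80% share, five tests | 80%, four |
|---|---|---|---|---|
| 99.0% | 19.4% | 22.5% | 44.5% | 47.0% |
| 99.5% | 29.6% | 32.9% | 51.2% | 52.8% |
| 99.8% | 42.6% | 45.3% | 56.2% | 56.9% |

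**Break-even.** Over five tests, false cases equal true cases at a specificity of about 99.70% for a 40% share, 99.54% for 50% and 97.97% for 80%.

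**Correlated errors.** In a latent-normal simulation with within-subject correlation 0.6, 99.0% specificity and negative results required at Screening and Day 0, about 193 false cases remain over five tests. Observed efficacy is 27% (40% share) or 50% (80% share). Requiring two consecutive positives cuts false cases to about 18 and brings observed efficacy to 54% or 59%, before any loss of true cases.

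**The case against.** **Confirmation exists outside the definition.** A positive antibody result leads to an RT-PCR and to blinded adjudication, and the charter is not shown. This stands in part: it would be wrong to say that positives go unexamined. But 3.7.2 does not use the swab result, and 7.11 describes the committee's task in terms of confirmed COVID-19 disease. For asymptomatic infection the only stated criterion is one symptom-free positive.

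**Same test and cut-off.** A reader might infer that entry and follow-up share one assay and one cut-off. The protocol uses the same general label, antibody to SARS-CoV-2, and names no assay, antigen or cut-off. Nothing here depends on it. If the test were the same, requiring earlier negatives would remove persistent cross-reactors and lower the risk.

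**The counts are a worst case.** Independent errors, full attendance and no symptom exclusion all inflate them. Intervals between in-window visits are 84 to 99 days, so some false positives would drop out because a symptom was reported. This stands. It reduces the bias but does not remove it.

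**The endpoint is minor.** It is exploratory, carries no p-value and feeds no trial decision. This stands and sets the priority.

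**Conclusion.** The definition is badly fixed: one positive serology suffices, and the RT-PCR and repeat serology that follow do not enter it. The direction of the bias is clear, provided test errors do not depend on treatment. Its size rests on the assumed specificity, asymptomatic share and true efficacy, and ranges from a few points (56% observed against 60%) to most of the effect (19% against 60%).

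A reader might conclude that false positives will match or outnumber true infections. The protocol does not support that as a general statement. It holds at a 40% share if specificity is about 99.7% or lower, but at the protocol's own upper figure of 80% it needs about 98%. Nor does this cast doubt on the main result: the primary endpoint requires RT-PCR plus fever or a symptom and is untouched. Priority is low; this is a cheap improvement to an exploratory analysis.

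**What to change.** In 3.7.2, for the main analysis of this endpoint, count an asymptomatic infection only when the first positive serology is confirmed by one of:

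- a positive RT-PCR at the assessment visit that it triggers;
- a second positive antibody result at the next scheduled serology visit;
- for a first positive at Day 393, a positive retest of the stored serum on a second assay.

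State that a negative RT-PCR alone does not rule out a case, because with visits about three months apart a swab will often be negative after a true past infection. Date the case at the first positive. Report the single-positive definition as a sensitivity analysis.

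The convalescent visit also has the instruction "Collect serum for SARS-CoV-2 antibody testing (Section 6.4.8"), but 6.1.2.8 limits that visit to subjects with confirmed infection. If its serum is to serve as confirmation, the two sections must be reconciled first; the rule above does not need it.

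The cost is a short addition to 3.7.2 and a few retests, using visits and sera already planned. The downside is that some true infections whose antibody wanes before the confirming sample will be lost. Section 1.2.1 itself cites falling IgG in early convalescence, so that number should be reported alongside the sensitivity analysis.

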3.8 SAFETY ASSESSMENT

Subjects will be followed for safety during the trial through scheduled clinic visits and phone calls. AEs, regardless of relationship to study drug, will be collected from the time of consent until 28 days post-dose 2 (i.e., Day 56). SAEs, MAAEs and AESIs will be collected from time of consent until EOS. SAEs, AESIs, and treatment-related AEs will be followed to resolution or stabilization. For the Phase 2 segment and at selected sites in the Phase 3 segment, solicited local and systemic AEs will be collected for 7 days following each dose using a participant diary.

Subjects will also be monitored for COVID-19 disease.

Please refer to the Schedule of Events (Table 3 and Table 4) for safety assessments to be performed.

3.9 IMMUNOGENICITY ASSESSMENT

Immunology blood samples will be collected at serial timepoints (see Schedule of Events, Table 3 and Table 4). Assays such as binding ELISA, pseudovirus-based neutralization assay, and ELISpot will be evaluated at serial timepoints.

4.0 **CLINICAL TRIAL POPULATION**

4.1 INCLUSION CRITERIA

4.1.1 PHASE 2 SEGMENT

- a. Able to provide informed consent and have signed Informed Consent Form (ICF) prior to screening procedures;
- b. Men and non-pregnant women 18 years of age or older;
- c. Assessed by the Investigator to be healthy based on medical history, vital signs and physical examination performed at Screening;
- d. Able and willing to comply with all study procedures;
- e. Working or residing in an environment with high risk of exposure to SARS-CoV-2 for whom exposure may be relatively prolonged or for whom personal protective equipment (PPE) may be inconsistently used, especially in confined settings:
 - 1. Retail/service workers/educators (restaurant waitresses/waiters and bar workers, store cashiers, hairdressers and barbers, veterinary staff, daycare workers, Transportation Security Administration screening staff, school teachers and college professors teaching in-person classes)
 - 2. Factory workers (when working in confined settings with large numbers of employees)
 - 3. Drivers providing bus, taxi or shared ride services (e.g., Uber, Lyft)
 - 4. User of public transportation (e.g., bus, train, subway) at least 3 times weekly
 - 5. Nursing home staff or correctional facility staff
 - 6. Retirement community residents or adult day program attendees who are regularly eating, socializing and/or exercising in common areas

INO-4800	COVID19-311
Inovio Pharmaceuticals, Inc.	Clinical Protocol

- 7. Person 51 years or older living in a multigenerational (at least 3 generations) household
- 8. First responders (emergency medical technicians, police who are regularly assigned on patrol. Note: Firefighters typically use face shields and other protective gear but may be considered if they regularly assist with medical emergencies in the field)
- Health care workers with prolonged patient interaction (includes nurses and nursing assistants, respiratory therapists, physical therapists, social workers, dentists and dental hygienists.) Physicians should not be enrolled unless they are assigned to dedicated COVID-19 treatment wards or other settings with prolonged exposure)

10. Others, if approved by the medical monitor;

- f. Screening laboratory results within normal limits for testing laboratory or are deemed not clinically significant by the Investigator;
- g. Must meet one of the following criteria with respect to reproductive capacity:
 - Women who are post-menopausal as defined by reported spontaneous amenorrhea for ≥ 12 months;
 - Surgically sterile or has a partner who is sterile (i.e., vasectomy in males or tubal ligation, absence of ovaries and/or uterus in females). In the case of vasectomy, subjects should wait six (6) months post-vasectomy prior to enrolling;
 - Use of medically effective contraception with a failure rate of < 1% per year when used consistently and correctly from screening until 3 months following last dose. Acceptable methods include:
 - o hormonal contraception including implants, injections or oral;
 - two barrier methods, e.g., condom and cervical cap (with spermicide) or diaphragm (with spermicide);
 - o intrauterine device or intrauterine system;
 - abstinence when this is the subject's preferred and usual lifestyle. Note: Periodic abstinence (e.g., calendar, ovulation, symptothermal, or postovulation methods) and withdrawal are not acceptable methods of contraception.

